6.1 Baseline Variable Collection

- Presence or absence of inclusion and exclusion criteria
- Date and time of randomization
- Date of symptom onset
- Admission data: date and time of presentation, origin (home, skilled nursing facility, rehabilitation/LTACH, nursing home, outside hospital, outside ICU), location at enrollment (ED, hospital ward, ICU)
- Demographics (age, sex, race, ethnicity, height, weight)

- Comorbidities: AIDS, Leukemia, Malignant Lymphoma, Hemiplegia, Cerebrovascular Disease, A prior myocardial infarction, Congestive Heart Failure, Peripheral vascular disease, Dementia, COPD, Connective tissue disease, Peptic ulcer disease, History of hypertension, HIV positive (without AIDS), Alcoholism, Coronary artery disease, Rapidly fatal disease, Solid tumor, Liver disease, Diabetes mellitus, Moderate to severe kidney disease
- Acute signs and symptoms: altered mental status, acute hypoxemic respiratory failure, liver function tests, renal function, coagulation studies, chest imaging results
- Sequential Organ Failure Assessment (SOFA)³³ at enrollment
- Chronic use of medication: corticosteroids, ACE inhibitors, angiotensin receptor blockers, non-steroids anti-inflammatory drugs, other
- Receipt of open label antivirals between hospital presentation and enrollment: chloroquine, hydroxychloroquine, remdesivir, lopinavir/ritonavir, other
- Receipt of open label immunomodulators between hospital presentation and enrollment: corticosteroids, tocilizumab, sarilumab, interferon β , other
- Receipt of convalescent plasma between hospital presentation and enrollment
- Receipt of azithromycin between hospital presentation and enrollment
- Receipt of invasive mechanical ventilation, non-invasive ventilation, high-flow nasal cannula, vasopressors, and oxygen therapy at enrollment
- Highest fraction of inspired oxygen, lowest arterial oxygen saturation, highest respiratory rate, lowest systolic blood pressure, highest heart rate in the 12 hours prior to enrollment
- Diagnosis of Acute Respiratory Distress Syndrome (ARDS) by Berlin Criteria³³ at enrollment
- COVID Ordinal Outcomes Scale at enrollment

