6.2 Assessments between Hospital Presentation and Hospital Discharge

- Specimen type, date, and result of SARS-CoV-2 testing conducted clinically
- Specimen type, date, and result of viral testing conducted clinically
- Specimen type, date, and result of bacterial testing conducted clinically
- Date and time of study drug administration and reason for missed doses
- COVID Ordinal Outcomes Scale on Days 2, 3, 4, 5, 8, 15, and 29
- SOFA on Day 3
- S/F ratio on Day 3
- Receipt of open label antivirals between randomization and hospital discharge: chloroquine, hydroxychloroquine, remdesivir, lopinavir/ritonavir, other
- Receipt of open label immunomodulators between randomization and hospital discharge: corticosteroids, tocilizumab, sarilumab, interferon β , other
- Receipt of convalescent plasma between hospital presentation and enrollment
- Receipt of azithromycin and other antibiotics between randomization and Day 8
- Clinically diagnosed deep vein thrombosis (DVT) or pulmonary embolism (PE) between hospital presentation and hospital discharge.
- Date and time of first receipt of supplemental oxygen (if applicable)
- Date and time of final receipt of supplemental oxygen (if applicable)
- Date and time of first receipt of high flow nasal cannula (if applicable)

- Date and time of final receipt of high flow nasal cannula (if applicable)
- Date and time of first receipt of non-invasive ventilation (if applicable)
- Date and time of final receipt of non-invasive ventilation (if applicable)
- Date and time of first receipt of invasive mechanical ventilation (if applicable)
- Date and time of final receipt of invasive mechanical ventilation (if applicable)
- Date and time of first receipt of extracorporeal membrane oxygenation (if applicable)
- Date and time of final receipt of extracorporeal membrane oxygenation (if applicable)
- Date and time of first receipt of vasopressors (if applicable)
- Date and time of final receipt of vasopressor (if applicable)
- Date and time of first meeting the Berlin Diagnostic Criteria for ARDS³³ (if applicable)
- Date and time of first ICU admission (if applicable)
- Date and time of final ICU discharge (if applicable)
- Date and time of hospital discharge (if applicable)
- Date of death (if applicable)

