Intensive care unit-free days (ICU-free days) to day 28 was defined as the number of whole calendar days alive and not admitted to an intensive care unit from 00:00 on the day of randomization through Study Day 29. Patients who died before Study Day 29 received a value of 0. If a patient survived to the first of discharge or Study Day 29 and was never admitted to an ICU, the number of ICU-free days was 28. If a patient was admitted to an ICU and survived to the first of discharge or Study Day 28, the number of ICU-free days was calculated as 28 minus the number of calendar days from the first ICU admission to final ICU discharge. Days on which the patient was not admitted to an ICU that occurred between days on which the patient was admitted to an ICU did not count towards the number of ICU-free days. Data on ICU use was censored at hospital discharge and the last observed status was carried forward (“in-hospital outcome”). That is, the analysis assumed that a patient who was discharged from the index hospitalization was not readmitted to an ICU between hospital discharge and Study Day 29.

Hospital-free days to Day 28

Hospital-free days to Day 28 was defined as the number of whole calendar days on which the patient was alive and not in the hospital from 00:00 on the day of randomization through Study Day 29. Patients who died before Study Day 29 received a value of 0. If a patient remained in the hospital during the index hospitalization through Study Day 29, the number of hospital-free days was 0. For patients

discharged from the index hospitalization prior to Study Day 28, the number of hospital-free days was calculated as 28 minus the duration of the index hospitalization in calendar days. Information readmissions occurring after discharge from the index hospitalization did not contribute to the calculation of the hospital-free days outcome.

Definition of Safety Outcomes (“all-location outcomes”)

1. Seizure – Between randomization and Study Day 29, as documented by treating clinicians in the electronic health record or reported by patient or surrogate on follow up telephone call.
2. Atrial arrhythmia - Between randomization and Study Day 29, as documented in the electronic health record or reported by patient or surrogate on follow up telephone call.

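### SAP Appendix B: the hospital-free-day formula subtracts the whole index stay although the outcome starts on the day of randomisation, and the free-day rules mix Study Day 28 with Study Day 29

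*SAP*

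**What the plan says.** SAP Appendix B, Hospital-free days to Day 28, defines the outcome as "the number of whole calendar days on which the patient was alive and not in the hospital from 00:00 on the day of randomization", and the sentence takes the count up to Study Day 29. Three rules follow:

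- Deaths: "Patients who died before Study Day 29 received a value of 0".
- Still in hospital: "If a patient remained in the hospital during the index hospitalization through Study Day 29, the number of hospital-free days was 0".
- Discharged before Study Day 28, by formula: "the number of hospital-free days was calculated as 28 minus the duration of the index hospitalization in calendar days".

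The last rule does not restrict the stay to days after randomisation.

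The general text in Appendix B, Days Free of Support, sets one window for all free-day outcomes, from the start of Study Day 1 to the end of Study Day 28. It credits days before the first support and days after the last day of support. The oxygen, ventilator and vasopressor formulas subtract the days from first to last support. The ICU formula subtracts the days from first ICU admission to final ICU discharge. None of the four names Study Day 1 as the earliest start. For a patient discharged while on oxygen, ventilation or vasopressors, support is carried forward to Study Day 29.

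SAP 4.2 allows randomisation up to 48 hours after hospital arrival. Protocol 6.1 records "Admission data: date and time of presentation, origin". Protocol 6.2, which covers the period from hospital presentation to discharge, records first and last dates of each support, of ICU care, and of discharge. SAP Appendix A analyses all five free-day outcomes by proportional odds.

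**The concern.** The definition and the formula measure different intervals. The definition begins on Study Day 1. The formula, as worded, begins when the index hospitalisation begins, and every patient is already in hospital or in an emergency department when randomised. One programmer could follow the definition and another the formula, and they would obtain different values from the same text.

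A proportional odds model uses the order of the values. A shift of one or two days can therefore reverse the order of two patients, tie a survivor with a death, or place a survivor below a death, since no floor at 0 is stated. The Day 28 and Day 29 endings can also produce a negative score.

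**Working it through.** **1. The constant 28.** Study Days 1 to 28 contain 28 - 1 + 1 = 28 days, which reproduces the constant in the formulas. Study Days 1 to 29 contain 29 days, which does not. The constant belongs to the window in Days Free of Support.

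**2. Hospital-free days.** Let k be the number of calendar dates from the start of the stay to Study Day 1. If the stay starts at arrival (assumption), the 48-hour limit gives k = 0, 1 or 2. Let d be the Study Day of discharge, 1 to 27, in a patient alive to Study Day 29.

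- Definition within Days 1 to 28: the discharge day is not a whole day out of hospital, so the value is 28 - d.
- Formula: the stay covers k + d dates, so the value is 28 - (k + d).
- Difference: -k.

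| k | d | Formula | Definition |
|---|---|---|---|
| 0 | 6 | 28 - 6 = 22 | 22 |
| 1 | 5 | 28 - 6 = 22 | 23 |
| 2 | 5 | 28 - 7 = 21 | 23 |
| 1 | 27 | 28 - 28 = 0 | 1 |
| 2 | 27 | 28 - 29 = -1 | 1 |

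Rows 1 and 3 change order: the patient discharged a day earlier scores lower. Row 4 ties with death and row 5 ranks below it.

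The documents give no distribution of the delay from arrival to randomisation. For illustration, if clock time of arrival is uniform and unrelated to the delay, a delay of H hours crosses H/24 midnights on average. The mean loss is then 0.5 day at 12 h, 1.0 at 24 h and 1.5 at 36 h.

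**3. Support or ICU care that began before Study Day 1.** Let the first date lie p dates before Study Day 1 and the last day be Study Day e, no later than 28. The literal formula gives 28 - (p + e); the window gives 28 - e. The shortfall is p. Oxygen from one date before Study Day 1 to Day 4 gives 28 - 5 = 23 instead of 24.

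**4. Support to Study Day 29.** Days Free of Support credits only days before the first and after the last support day, so both end days count as supported. For support from Day s (1 to 28) to Day 29:

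- Literal: 28 - (29 - s + 1) = s - 2.
- Within Days 1 to 28: 28 - (28 - s + 1) = s - 1.

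For s = 10 this is 8 instead of 9. For s = 1 it is -1 instead of 0.

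**5. Discharge on Study Day 28.** The formula stops at discharge on Day 27, and the zero rule needs a stay to Day 29. Neither covers Day 28. The Day 28 window gives 28 - 28 = 0; the Day 29 ending in the definition sentence would leave one free day.

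**The case against.** The strongest reply is that the SAP makes its intent plain. Appendix B calls randomisation time zero for all assessments. Days Free of Support starts every free-day count on Study Day 1, and the hospital definition does so again. SAP 7.5 limits these outcomes to information after randomisation. On that reading the formula is shorthand for the part of the stay inside the window, and a programmer who follows these texts obtains the right value. A score of -1 would also stand out in routine checks. The point about intent stands. It does not correct the formula, which is the only computing rule given for discharged patients, and a score of 21 in place of 23 would not stand out.

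The size also depends on when the stay starts. SAP 4.1 admits patients still in an emergency department, so counting from inpatient admission would shrink k. This stands, and the shortfall of 0 to 2 days is conditional on counting from arrival. In the other direction, Protocol 6.1 lists an outside hospital as an origin; if such a stay were counted, k could exceed 2.

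A reader might go further and infer that the SAP leaves open whether the end days of a support period count. The documents do not support that: crediting only days before the first and after the last support day implies inclusive counting, and the vasopressor text treats any day with a listed drug as a vasopressor day.

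**Conclusion.** The concern holds as a conflict between definition and formula. If the stay is counted from arrival, hospital-free days are 0, 1 or 2 days too low, and the error falls only on patients discharged before Study Day 28, alive to Study Day 29, and randomised on a later date than arrival. The support and ICU formulas share the fault when coded literally for patients whose first date precedes Study Day 1. Separately, the Day 29 endings cost one day for support that runs to Day 29, and discharge on Day 28 needs a rule. The documents give no frequency for any of these groups.

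A reader might infer that the treatment comparison is biased or that the main result is at risk. Neither follows. Days before randomisation are fixed before allocation, so they add noise and rank errors and favour neither arm in expectation. The Day 29 rule is the same in both arms and creates no difference where none exists. The primary outcome, sample size and stopping guidelines do not use these variables. Severity is minor. Confidence is high for the conflict in wording and lower for its size in practice.

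**What to change.** For all five free-day outcomes, state one rule in SAP Appendix B:

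- Count inclusive calendar days in hospital, in ICU or on support within Study Days 1 to 28 only.
- Start at the later of admission (or first support) and Study Day 1.
- End at the earlier of discharge (or last support, including carry-forward) and Study Day 28.
- Free days = 28 minus that count, with a floor of 0. Keep the value 0 for deaths.

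Define the start of the index hospitalisation. Change Study Day 29 to Study Day 28 in the counting and carry-forward sentences. State that discharge on Study Day 28 scores 0. Survivors hospitalised or supported throughout then tie with deaths at 0, as the SAP already provides for patients who stay in hospital to Study Day 29, and none ranks below a death.

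The cost is Appendix B wording and derivation code. All dates needed are already collected.

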- Safety Outcomes: seizure, atrial or ventricular arrhythmia, cardiomyopathy, cardiac arrest, aspartate aminotransferase or alanine aminotransferase levels that are greater than twice the local upper limit of normal, acute pancreatitis (defined by a clinically obtained lipase level above the local upper limit of normal), stage II or greater acute kidney injury according to KDIGO criteria³⁴, receipt of new renal replacement therapy, symptomatic hypoglycemia, neutropenia, lymphopenia, anemia, thrombocytopenia, or severe dermatologic reaction (e.g., Steven's Johnson Syndrome)
- Patient destination at discharge

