9.1.1 Potential risks of receiving hydroxychloroquine

Potential risks of receiving hydroxychloroquine can be classified based on their severity as Major or Minor. Major potential risks of receiving hydroxychloroquine include:

- 1) Neurological System
 - a) Seizure – Hydroxychloroquine can lower the seizure threshold and co-administration of hydroxychloroquine with other medications known to lower the seizure threshold has been reported to increase the risk of seizures. This trial protocol excludes patients with a seizure disorder.
 - b) Psychosis – A small number of case reports describe psychosis in patients on long-term treatment with hydroxychloroquine,³⁹ but has not been described with short-term treatment.
 - c) Suicidal behavior - Suicidal behavior has been rarely reported in patients on long-term treatment with hydroxychloroquine for rheumatologic disorders,⁴⁰ but not with short-term therapy.
- 2) Circulatory system
 - a) Cardiac arrhythmias
 - i) Ventricular arrhythmias and torsades de pointes – Hydroxychloroquine can prolong the QT interval and ventricular arrhythmias and torsades de points have been reported in patients taking hydroxychloroquine. This trial protocol excludes patients with a prolonged QTc on baseline EKG and history of prolonged QTc syndromes, assesses the QTc after receipt of study drug, monitors daily for co-administration of medications that prolong the QTc and specifies criteria for stopping the study drug based on prolonged QTc.
 - ii) Cardiomyopathy, sick sinus syndrome, atrioventricular block, or bundle branch block – Cardiomyopathy and conduction system disease have rarely been reported among patients on long-term hydroxychloroquine,⁴¹ but have not been reported among patients receiving less than 3 months of therapy.
- 3) Digestive system
 - a) Liver injury – Fulminant hepatic failure has been reported in at least two cases from long-term administration of hydroxychloroquine.⁴² Porphyrria cutanea tarda appears to be a risk factor for liver injury from hydroxychloroquine. This trial protocol excludes patients with porphyria cutanea tarda.
 - b) Increased cyclosporine or digoxin levels – hydroxychloroquine can increase levels of cyclosporine or digoxin for patients being co-administered these medications. This trial protocol monitors daily for receipt of medications that interact with hydroxychloroquine and notifies treating clinicians about potential medication interactions.
- 4) Endocrine system

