11.2 Safety Monitoring

Assuring patient safety is an essential component of this protocol. Each participating investigator has primary responsibility for the safety of the individual participants under his or her care. The Investigators will determine daily if any adverse events occur during the period from enrollment through **study day 7** (48 hours after completion of the study drug) or hospital discharge, whichever occurs first and will determine if such adverse events are reportable. Thereafter, adverse events are not required to be reported unless the investigator feels the adverse event was related to study drug or study procedures.

The following adverse events will be considered reportable and thus collected in the adverse event case report forms:

- Serious adverse events
- Non-serious adverse events that are considered by the investigator to be related to study procedures or of uncertain relationship (Appendix C)
- Events leading to permanent discontinuation of study drug

Study-specific clinical outcomes (Primary, Secondary and Safety Outcomes and Assessments During the Study), including serious outcomes such as organ failures and death, are systematically recorded in the case report forms and are exempt from adverse event reporting unless the investigator deems the event to be related to the administration of study drug or the conduct of study procedures (or of uncertain relationship) as outlined in Appendix C.

After randomization, adverse events must be evaluated by the investigator. If the adverse event is judged to be reportable, as outlined above, then the investigator will report to the CCC their assessment of the potential relatedness of each adverse event to the study drug or protocol procedure via electronic data entry. Investigators will assess if there is a reasonable possibility that the study procedure caused the event, based on the criteria outlined in Appendix C. Investigators will also consider if the event is unexpected. Unexpected adverse events are events not listed in the study protocol and the investigator brochure for Hydroxychloroquine. Investigators will also determine if adverse events are unanticipated given the patient's clinical course, previous medical conditions, and concomitant medications.

If a patient's treatment is discontinued as a result of an adverse event, study site personnel must also report the circumstances and data leading to discontinuation of treatment in the adverse event case report forms.

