6.3 Safety Outcomes

- Seizure
- Atrial or ventricular arrhythmia
- Cardiac arrest
- Elevation in aspartate aminotransferase or alanine aminotransferase to twice the local upper limit of normal
- Acute pancreatitis
- Acute kidney injury
- Receipt of renal replacement therapy
- Symptomatic hypoglycemia
- Neutropenia, lymphopenia, anemia, or thrombocytopenia
- Severe dermatologic reaction

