Atrial arrhythmia	Safety Outcome	Binary	Simple logistic regression

Ventricular arrhythmia	Safety Outcome	Binary	Simple logistic regression
Cardiac arrest	Safety Outcome	Binary	Simple logistic regression
Elevation in aspartate aminotransferase or alanine aminotransferase above 2x upper limit of normal	Safety Outcome	Binary	Simple logistic regression
Acute pancreatitis	Safety Outcome	Binary	Simple logistic regression
Acute kidney injury	Safety Outcome	Binary	Simple logistic regression
Receipt of renal replacement therapy	Safety Outcome	Binary	Simple logistic regression
Symptomatic hypoglycemia	Safety Outcome	Binary	Simple logistic regression
Neutropenia	Safety Outcome	Binary	Simple logistic regression
Lymphopenia	Safety Outcome	Binary	Simple logistic regression
Anemia	Safety Outcome	Binary	Simple logistic regression
Thrombocytopenia	Safety Outcome	Binary	Simple logistic regression
Severe dermatologic reaction	Safety Outcome	Binary	Simple logistic regression

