3. Ventricular arrhythmia - ventricular tachyarrhythmia (ventricular fibrillation or ventricular tachycardia) treated with a medication or electrical cardioversion or debrillation between randomization and Study Day 29, as documented in the electronic health record or reported by patient or surrogate on follow up telephone call.
4. Cardiac arrest - Between randomization and Study Day 29, as documented in the electronic health record or reported by patient or surrogate on follow up telephone call. Does not include expected cardiac arrests occurring as a part of the dying process for patients on comfort measures.
5. Elevation in aspartate or alanine aminotransferase to twice the upper limit of normal – Between randomization and Study Day 29, as documented in the electronic health record or reported by patient or surrogate on follow up telephone call.
6. Acute Pancreatitis – Clinically-obtained lipase level above the local upper limit of normal between randomization and day 29.
7. Acute Kidney Injury – Stage II or greater acute kidney injury by Kidney Disease Improving Global Outcomes (KDIGO) Criteria between randomization and day 29, defined as any of the following:
 - a. Creatinine at least 2.0 times the baseline value
 - b. Increase in serum creatinine above 4.0 mg/dl
 - c. Urine output less than 0.5 ml/kg/h for at least 12 hours
 - d. Initiation of new renal replacement therapy
8. Receipt of renal replacement therapy – Between randomization and Study Day 29, as documented by treating clinicians in the electronic health record or reported by patient or surrogate on follow up telephone call.
9. Symptomatic hypoglycemia – Between randomization and Study Day 29, as documented by treating clinicians in the electronic health record or reported by patient or surrogate on follow up telephone call.
10. Neutropenia – Clinically-obtained absolute neutrophil count < 1000 (cells/mm³) between randomization and Study Day 29
11. Lymphopenia – Clinically obtained absolute lymphocyte count < 1000 (cells/mm³) between randomization and Study Day 29.
12. Anemia – Clinically-obtained hemoglobin < 12.0 g/dL between randomization and Study Day 29.

13. Thrombocytopenia – Clinically-obtained platelet count < 50 (cell/mm³; in thousands) between randomization and Study Day 29.

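### The SAP counts ventricular arrhythmia only when treated and has no cardiomyopathy outcome, so such events judged unrelated to study drug would be missing from the planned by-arm tables

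*SAP*

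**What the plan says.** **Ventricular arrhythmia.** Protocol 5.3 and SAP 6.3 carry the same unqualified entry, "Atrial or ventricular arrhythmia". SAP Appendix A has a separate row, "Ventricular arrhythmia", analysed as a binary outcome by unadjusted logistic regression. The treatment condition appears only in SAP Appendix B, item 3: "ventricular tachyarrhythmia (ventricular fibrillation or ventricular tachycardia) treated with a medication or electrical cardioversion or debrillation". The item just before it has no such condition: "Atrial arrhythmia - Between randomization and Study Day 29, as documented in the electronic health record", or as reported by telephone.

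**Cardiomyopathy.** Protocol 6.2 includes it in the safety outcomes to be collected: "seizure, atrial or ventricular arrhythmia, cardiomyopathy, cardiac arrest". It is not in protocol 5.3, SAP 6.3 or SAP Appendices A, B and C.

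**Adverse event reporting.** Protocol 11.2 says that study-specific outcomes, including safety outcomes and on-study assessments, "are systematically recorded in the case report forms and are exempt from adverse event reporting unless the investigator deems the event to be related" or of uncertain relationship. Protocol Appendix C.3 repeats the exemption and names arrhythmia among its examples. SAP 7.6 reports adverse events by arm.

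**The concern.** Ventricular arrhythmia is the harm behind much of the trial's safety design. Protocol 9.1.1 states: "Hydroxychloroquine can prolong the QT interval and ventricular arrhythmias and torsades de points have been reported in patients taking hydroxychloroquine". Protocol 3.3 justifies exclusions by torsades de pointes, 4.5 requires a QTc check after the first dose, and 4.6 has a QTc rule for study drug.

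Under SAP item 3, a run of ventricular tachycardia that ends by itself is not an event. Whether an episode is treated depends partly on clinician practice, so the definition mixes occurrence with management. A reader of a results row labelled simply as ventricular arrhythmia would take it to mean any such arrhythmia, as the protocol's list suggests.

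The adverse event table would normally catch what a narrow outcome definition leaves out. Here it may not, because the same class of event is exempt from adverse event reporting when judged unrelated. In acutely ill patients, single-case attribution by a blinded investigator is a weak filter. By-arm counts that do not depend on attribution are the stronger evidence.

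**Working it through.** The plan states no figure on this point, so the check compares the texts and then traces where an event would be tabulated.

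**Step 1. Where each outcome appears**

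| Place | Ventricular arrhythmia | Cardiomyopathy |
|---|---|---|
| Protocol 5.3 | named, no condition | absent |
| Protocol 6.2 | named, no condition | named |
| SAP 6.3 | named, no condition | absent |
| SAP Appendix A | own row, no condition | absent |
| SAP Appendix B | treated VF/VT only | absent |
| SAP Appendix C | not listed | absent |

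For ventricular arrhythmia, Appendix B is narrower than the four other places that name it. For cardiomyopathy, the SAP agrees with protocol 5.3, so the mismatch begins inside the protocol, between 5.3 and 6.2.

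**Step 2. Where an event after randomization would be tabulated**

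| Event | SAP safety table | Adverse event table |
|---|---|---|
| VF/VT, treated | yes | only if related, uncertain or otherwise reportable |
| VF/VT, untreated, judged related or uncertain | no | yes |
| VF/VT, untreated, study drug permanently stopped because of it | no | yes |
| VF/VT, untreated, judged unrelated, no permanent stop | no | no |
| Cardiomyopathy, judged unrelated, no permanent stop | no | no |

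The gap is the last two rows. Protocol Appendix C.3 does not name cardiomyopathy among its examples, so its exemption rests on the general clause in 11.2. Timing matters too: the SAP safety outcomes run to Study Day 29, whereas protocol 11.2 requires general adverse event reporting only to study day 7 or discharge, whichever is first. After that, only events the investigator considers related must be reported.

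**Step 3. Size**

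The documents give no rate of ventricular arrhythmia or cardiomyopathy and no proportion treated. Let *f* be the proportion of ventricular episodes that are treated. The SAP then keeps *f* × (all events) in each arm.

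As an illustration only, assume 510 / 2 = 255 patients per arm and true risks of 4% and 2%:

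- All events: 255 × 0.04 = 10.2 against 255 × 0.02 = 5.1.
- *f* = 0.3: 3.06 against 1.53.
- *f* = 0.5: 5.1 against 2.55.
- *f* = 0.7: 7.14 against 3.57.

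With the same *f* in both arms, the ratio stays at 2 throughout. What is lost is events, and hence precision. For cardiomyopathy the SAP keeps none, whatever the rate.

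**The case against.** The strongest reply is that this is a definition and not a contradiction. The protocol names ventricular arrhythmia without defining it. SAP section 1 assigns definitions to Appendix B, which also sets thresholds for neutropenia, anemia and thrombocytopenia that the protocol lacks. A treated-event definition is defensible for an outcome collected partly by telephone. The case report form is not among the documents and may ask only about treated episodes. This stands in part: the SAP may define the outcome, but SAP 6.3 and Appendix A then carry a label wider than what is counted, no reason is given, and the atrial item is handled differently.

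Other coverage also exists. SAP 7.7 presents QTc by arm at 24-48 hours, SAP Appendix C tabulates reasons for missed doses, and cardiac arrest is a separate outcome. Protocol Appendix C has the DSMB review clinical outcomes. These limit the consequence but do not replace a by-arm count of ventricular arrhythmia.

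On cardiomyopathy, protocol 9.1.1 lists it under major risks but adds that it has not been reported with under 3 months of therapy; treatment here lasts 5 days. It is therefore secondary to the arrhythmia point.

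A reader might infer three stronger things that the documents do not support:

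- *That the SAP definition hides an imbalance.* Clinicians are blinded, nothing shows that treatment of episodes would differ by arm, and the illustration keeps its ratio.
- *That events causing only a temporary hold of study drug escape reporting.* Protocol 11.2 lists permanent discontinuation, but 4.6 sends adverse events behind a temporary stop to the adverse event guidelines as well.
- *That venous thromboembolism is another dropped safety outcome.* Protocol 6.2 collects "Clinically diagnosed deep vein thrombosis (DVT) or pulmonary embolism (PE) between hospital presentation and hospital discharge", but as a data item outside the safety list. Its window opens before randomization and no diagnosis date is specified.

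**Conclusion.** The point holds as a mismatch in scope with a limited reporting gap. SAP Appendix B narrows ventricular arrhythmia to treated VF/VT under a label that elsewhere has no such limit, and cardiomyopathy is collected under protocol 6.2 without any planned analysis. Untreated ventricular arrhythmia or cardiomyopathy that is judged unrelated and does not end study drug permanently would appear in neither planned by-arm table.

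It would be wrong to call these events lost or unreported outright. The protocol has them recorded and the DSMB can see them. The exemption is conditional, and Appendix C.3 uses a related ventricular arrhythmia as its own example of an event that is both recorded and reported.

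The conclusion assumes that the case report form follows protocol 6.2 and captures ventricular arrhythmia whether or not treated. If it captures only treated episodes, the label should say so and the limitation should be stated. The size of the under-count cannot be derived from the documents. The change is worth making because the outcome is central to the drug's expected harm and the cost is small.

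**What to change.** 1. In SAP 6.3 and Appendices A and B, define the outcome as any documented ventricular tachycardia (including torsades de pointes) or ventricular fibrillation after randomization. Tabulate it by arm, with treated episodes as a sub-row.
2. If the case report form records only treated episodes, keep the definition, label the row *treated ventricular arrhythmia* wherever it appears, and state that untreated episodes are not captured.
3. Reconcile protocol 5.3 with 6.2 on cardiomyopathy, and add a by-arm cardiomyopathy row to the SAP.

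The cost is SAP wording, one protocol list entry and two table rows, from data that protocol 6.2 already calls for. The downside is that short untreated runs are found more often in monitored patients, so the any-event count depends partly on intensity of monitoring. The treated sub-row stays for that reason.
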